6.6.7 Emergency Unblinding of Treatment Assignment

Not applicable to this open-label study.

7 Visit Schedule and Assessments

Table 9 lists all of the assessments and indicates the visits with an “X” and when they are to be performed. All data obtained from these assessments must be supported in the patient’s source documentation.

Table 9 Visit Evaluation Schedule

	Screening - 35	Baseline -7 to -1	Cycle 1 (28 days)		Cycle 2 (28 days)		Cycle 3 (28 days)		Subsequent Cycles (28 days)	End-of- Study Treatment	Endpoint Follow-Up ^a
Visit number	1a	1b	2	3	4	5	6	7	8, 9	Last visit	
Day of cycle			1	15	1	15	1	15	1	Last day	
Demography/informed consent	X										
Inclusion/exclusion criteria	X		X								
Medical history/current medical conditions	X		X								
Diagnosis and extent of cancer	X										
Prior antineoplastic therapy	X										
Vital signs ^a	X	X	X		X		X		X	X	
Height, weight	X										
Physical examination/neurological assessment ^b	X		X		X		X		X	X	
Karnofsky Performance Status	X	X	X		X		X		X	X	
Hematology ^c	X	X	X	X ^c	X	X ^c	X	X ^c	X	X	
Coagulation ^d	X				X						
Serum chemistry ^e	X	X	X		X		X		X	X	
Serum lipid profile ^f	X	X	X		X		X		X	X	
Urinalysis ^g	X	X									
Serum pregnancy test ^h	X	X									
HBV-DNA & serology, HCV RNA-PCR ^r	X		X		X		X	X	X		X
CT scan or MRI of chest, abdomen, and pelvis ⁱ If the CT Scan was performed during the screenig (in the range of 35 days) it does not need to be performed again at baseline	X	X					X			Every 12 weeks after Visit 6	X
Brain MRI/brain CT scan ^k	X	X	As described in footnote ^k								
Bone scan ^l	X	X	As described in footnote ^l								
Electrocardiogram ^m	Electrocardiograms are to be performed at the investigator's discretion as clinically indicated										
Pulmonary function tests ⁿ	X	X	Pulmonary function tests to be performed as described in footnote ⁿ								

Table 9 Visit Evaluation Schedule

	Screening - 35	Baseline -7 to -1	Cycle 1 (28 days)		Cycle 2 (28 days)		Cycle 3 (28 days)		Subsequent Cycles (28 days)	End-of- Study Treatment	Endpoint Follow-Up ^a	
Visit number	1a	1b	2	3	4	5	6	7	8, 9	Last visit		
Day of cycle			1	15	1	15	1	15	1	Last day		
Concomitant medications ^o	X	X	X	X	X	X	X		X	X	X	X
Adverse event ^p	X	X	X	X	X	X	X		X	X	X	X
Imaging for tumor evaluation ^q							X			Every 12 weeks after Visit 6	X	
RAD001 administration ^r			Daily administration									
Study completion ^s											X	
Follow-up and survival ^t												X
Post-discontinuation antineoplastic therapies ^u												X

^a Vital signs will be collected at screening and repeated on Day 1 of every treatment cycle and at the end of-the-study (within ≤2 weeks).

^b A complete physical examination includes a neurological examination. All significant findings will be noted on the Relevant Medical History pages or Adverse Event pages of the case report form (CRF). If a skin lesion or lesions are selected as target lesions, they must be clearly photographed and measured with a measuring device (a caliper or ruler) in clear focus to allow the size of the lesion(s) to be determined from the photograph. Serial photographs from the skin lesion(s) must be performed at every physical exam visit. Copies of the serial photographs must be submitted with the radiological assessments for radiology review.

^c Hematology tests must include: hemoglobin, hematocrit, platelets, total white blood count (WBC), and differential. Hematological tests will be performed at screening and on Day 1 (prior to administration of the study drug) of each treatment cycle. Hematological tests may also be performed on Day 15 of the first 3 treatment cycles at the investigator’s discretion and according to local practice. Subsequently, on Day 1 (of every treatment cycle) or as medically necessary and at discontinuation from the study drug (within ≤2 weeks).

^d The prothrombin time will be performed at screening and on Day 1 of Cycle 2. Prothrombin time will be repeated as clinically indicated and will be reported as international normalized ratio (INR).

^e Serum blood chemistry evaluations must include: lactate dehydrogenase (LDH), fasting glucose, magnesium, sodium, potassium, chloride, creatinine, blood urea nitrogen, albumin, total protein, alanine aminotransferase (ALT), aspartate aminotransferase (AST), total bilirubin, gamma-glutamyl-transferase (GGT), alkaline phosphatase, urea, uric acid, serum calcium, and serum corrected calcium (measured at screening only). These assessments will be performed at screening and on Day 1 of every treatment cycle and at the time of discontinuation from the study drug (within ≤2 weeks).

^f Serum lipid profile includes: total cholesterol, triglycerides, low-density lipoprotein, and high-density lipoprotein. These assessments will be performed at screening and on Day 1 of every treatment cycle and at the time of discontinuation from the study drug (within ≤2 weeks).

^g Urine analysis assessments include: gross or a microscopic urine exams. A dipstick assessment includes: specific gravity, pH, protein, glucose, bilirubin, ketones, blood cells, and leukocytes. The urinalysis will be performed at screening and as clinically indicated. Urine specimens will be sent to the local laboratory for analysis.

^h Serum urine pregnancy test. Females of childbearing potential must have a serum or urine pregnancy test performed within 7 days prior to the first dose of study drug.

ⁱ A computerized tomography (CT) scan or magnetic resonance image (MRI) of the chest/abdomen and pelvis will be performed at screening (≤35 days) prior to the first dose of study drug and at 8 weeks (±1 week). Thereafter, a CT scan or MRI of the chest/abdomen and pelvis will be performed every 12 weeks (±1 week), and at the time of discontinuation of the study drug (within 2 weeks).

^j A chest x-ray can be performed at the investigator’s discretion, if there is a suspicion of non-infectious pneumonitis.

^k A brain MRI or brain CT scan will be obtained within 2 weeks of the first dose of study drug and as clinically indicated if the patient develops signs or symptoms of central nervous system (CNS) involvement. If brain metastases are present at baseline, brain MRI/brain CT scan will be performed every 8 weeks during the study.

^l A bone scan will be obtained at screening (within 3 weeks of the first dose of study drug) and as clinically indicated if the patient develops signs or symptoms of bone disease. If bone metastases are present at baseline, the bone scans will be performed every 12 weeks (±1 week) during the study.

^m Standard 12-lead electrocardiograms are to be performed at the investigator’s discretion according to local practice, or if there are signs and symptoms of cardiotoxicity. Any significant findings will be noted

Table 9 Visit Evaluation Schedule

	Screening - 35	Baseline -7 to -1	Cycle 1 (28 days)		Cycle 2 (28 days)		Cycle 3 (28 days)		Subsequent Cycles (28 days)	End-of- Study Treatment	Endpoint Follow-Up ^a
Visit number	1a	1b	2	3	4	5	6	7	8, 9	Last visit	
Day of cycle			1	15	1	15	1	15	1	Last day	

- on the Relevant Medical History or Adverse Event pages of the CRF.
- ^a Pulmonary function tests (including spirometry, diffusion capacity of carbon monoxide, and room air O₂ saturation at rest) will be performed at screening per investigator discretion, and at the end of the study (≤2 weeks) and as medically necessary if there is evidence of non-infectious pneumonitis. A bronchoscopy with a biopsy and/or bronchoalveolar lavage will be performed when medically necessary for decisions regarding patient care. The results will be recorded on the appropriate CRF page.
 - ^o Record all medications given ≤30 days prior to study entry on the Concomitant Medications/Significant Non-Drug Therapies Prior to the Start of the Study CRF page. After the start of the study, concomitant medications must be recorded on the Concomitant Medications/Significant Non-Drug Therapies CRF page.
 - ^p All adverse events (AEs) occurring after the start of the study, even if the event is not considered to be related to the study drug, must be documented on the Adverse Event CRF page.
 - ^q Information on all target tumor and non-target lesions will be collected at screening. Subsequently, radiological assessments (to follow the target and non-target lesions identified at baseline) will be performed at 8 weeks (±1 week). In the absence of progressive disease, assessments will continue every 12 weeks (±1 week) until the start of new anticancer therapy and at the End-of-Study Visit (within 1 week of stopping treatment) or until death. Observation of tumor response (partial or complete response) warrants a confirmation no sooner than 4 weeks. The same type of scan (CT or MRI) used at screening must be used for all subsequent follow-up assessments.
 - ^r RAD001 10 mg daily dosing will begin on Day 1 of Cycle 1. Treatment with the study drug will continue until disease progression, unacceptable toxicity, withdrawal of consent, death, etc.
 - ^s Patients who discontinue the study drug will have end-of-study evaluations performed on that day or within 2 weeks of discontinuation of the study drug.
 - ^t All patients will have a follow-up visit 28 days after the last dose of RAD001. During this visit, AE and serious adverse event information occurring since the last dose of study drug will be collected and recorded on the appropriate CRF pages. All patients who are discontinued from the study drug for any reason will continue to have tumor assessments until the start of any new anticancer therapy.
 - ^u After discontinuation of the study drug, the investigator or his/her designee will collect information on the initiation of new anticancer therapies given after the last dose of study drug.
 - ^v All patients will be screened for HBV-DNA, HBV serologic markers and HCV RNA-PCR. It is highly recommended that patients positive for HBV-DNA or HBsAg receive prophylactic antivirals for 1-2 weeks prior to receiving study drug. The antiviral treatment should continue throughout the entire study period and for at least 4 weeks after the last dose of study drug. Monitoring for HBV reactivation, according to [Table 6-5](#), will only require the measurement of HBV-DNA from Visit 2 onwards. Patients who are HBV-DNA / HBsAg positive at screening will be monitored every cycle. Patients who are HBV-DNA and HBsAg negative at screening (and not receiving prophylaxis) but HBsAb or HBcAb positive will be monitored every cycle. Follow-up testing for HCV RNA-PCR will be performed every cycle only if the patient has a history of HCV or is positive at baseline, or both. If there is no history of HCV and HCV RNA-PCR test is negative at baseline, no follow-up testing is required.

7.1 Visit Windows

For Cycles 1, 2, and 3, visits will be on the 1st and 15th day (± 5 days) of each 28-day cycle. For each subsequent cycle, patients will return to the site on the 1st day (± 5 days) of each 28-day cycle.

7.2 Information to be Collected on Screening Failures

Patients who are screened and do not meet all entry criteria will not receive the first dose of RAD001. Such patients are considered to be screen failures. The reason for not being started on RAD001 will be entered on the Screening Log CRFs. Screen failures are not entered into the clinical data base.

7.3 Patient Demographics/Other Baseline Characteristics

Data will be collected on patient characteristics, including demographic information (age, sex, race, weight) and other background or relevant medical history (cancer history and extent of cancer, prior anticancer therapies) and any other assessments that are done for the purpose of determining eligibility for inclusion in the study (i.e., Karnofsky Performance Status, complete physical examination including a neurological assessment, vital signs, hematology, blood chemistries including coagulation studies and a serum lipid profile, urinalysis, pregnancy test [only required for females of childbearing potential], a brain MRI or a brain CT scan, electrocardiogram [ECG]).

Urinalysis and the pregnancy test are only performed at either screening or baseline for eligibility, but are not repeated after the patient has started the study drug or at discontinuation from the study.

The patient population will be stratified by prior cytokine therapy.

7.4 Treatments

RAD001 10 mg daily dosing will begin on Day 1 of Cycle 1. This study does not have a fixed treatment duration. Patients will receive study treatment until disease progression or until unacceptable toxicity is observed. Information on drug exposure will be collected on the Dosage Administration Record CRF page. Concomitant medications/significant non-drug therapies prior to start (≤ 30 days) and after the start of study treatment will be recorded on the appropriate CRF pages. Patient screening and randomization data will be stored on the appropriate CRF pages.

7.5 Efficacy

The primary efficacy endpoint is PFS as defined in [Section 10.4.1](#). Secondary efficacy endpoints are OS, disease control rate (SD + PR + CR), the ORR (CR + PR) as defined in Section 10.5.1, as well as response duration.

7.5.1 Radiological Assessment of Tumor(s)

Tumor response, stable disease, and progression, will be assessed using the RECIST criteria (see [Post-Text Supplement 1](#) for complete details). A CT scan or MRI of the chest/abdomen

and pelvis will be obtained at screening (≤ 35 days) prior to the first dose of RAD001 and periodically as indicated in Table 9. Tumor response will be assessed at 8 weeks (± 1 week) and every 12 weeks (± 1 week) thereafter until determination of disease progression (by the local radiologist) and at the end of the study.

All patients who are discontinued from RAD001 for any reason (i.e., documented disease progression by the investigator, an AE or SAE, or administrative reasons, etc.) will continue to have tumor assessments until the start of new anticancer therapy.

At screening (≤ 35 days prior to the first dose of RAD001), all patients must have a CT scan with contrast or MRI with contrast of the chest, abdominal, and pelvic area. Patients who are allergic/sensitive to the radiographic contrast media used in CT scans and MRIs may have a CT scan of the chest without contrast and a MRI of the abdomen and pelvis without contrast. The same imaging modality used at screening must be used for all subsequent follow-up assessments.

Ultrasound scans cannot be used to measure tumor lesions.

All patients should have at least one measurable disease lesion by CT scan or MRI or by physical exam. Physical examination findings, such as skin lesions, must be photographed (color photography) using a digital camera. Subcutaneous nodules will be measured with a caliper or a ruler. If skin lesions are used for assessment of disease, at least one skin lesion should be biopsied to establish the malignant nature of the lesions. The site must document on the Tumor Assessment Comments CRF page that a biopsy of at least one skin lesion confirming the presence of metastatic disease has been obtained or was available for this purpose.

Measurable disease lesions must be accurately measured in at least one dimension with the longest diameter ≥ 20 mm using conventional techniques, or ≥ 10 mm with spiral CT scan (with a minimum lesion size no less than double the slice thickness). Conventional CT and MRI should be performed with contiguous cuts of 7.5 mm or less in slice thickness. Spiral CT should be performed using a 5 mm or less contiguous reconstruction algorithm (this specification applies to tumors of the chest, abdomen, and pelvis).

All measurable lesions up to a maximum of five lesions per organ and 10 lesions in total, representative of all involved organs should be identified as target lesions. The target lesions will be measured and recorded at baseline and during the course of the study. The target lesions should be selected on the basis of their size (lesions with the longest diameters) and suitability for accurate repeated measurements. A sum of the longest diameter for all target lesions will be calculated and reported as the baseline sum of the longest diameter.

If a very small lesion cannot be reliably measured because of its size, it is recommended to enter the minimum lesion size (i.e., 5 mm for spiral CT). In other cases where the lesion cannot be reliably measured for reasons other than its size (i.e., borders of the lesion are confounded by neighboring anatomical structures), no measurement should be entered and the lesion cannot be evaluated.

A target lesion that resolves from baseline must be assigned a size of 0 mm when documenting on the patient's RECIST CRF page. Refer to [Supplement 1](#) for additional target and non-target lesion reporting guidelines.

Partial response requires at least a 30% decrease in the sum of the longest diameters of all target lesions, taking as reference the baseline sum of the longest diameters.

Complete response requires a disappearance of all target and non-target lesions. If an initial observation of partial or complete response is made, a confirmation scan is required no sooner than 4 weeks.

In case of an unscheduled or delayed tumor assessment (i.e., to confirm a PR/CR or due to any other reason), subsequent tumor assessments must be performed according to the originally planned scheme from baseline, i.e., every 12 weeks from the time of the second assessment at 8 weeks.

Disease progression is either 1) a 20% increase in the sum of the longest diameter of all target lesions, taking as reference the smallest sum of the longest diameters of all target lesions recorded at or after baseline, or 2) the appearance of a new lesion, or 3) the unequivocal progression of non-target lesions overall. Patients who had suspected clinical symptoms of disease progression should be immediately evaluated with a physical examination and imaging (CT scan or MRI) assessment for objective evidence of disease progression.

7.5.2 Imaging Procedures

To ensure a valid comparison of tumor data and uniformity in the assessment of tumor response during the study, the following procedure must be implemented at the study site:

- All lesions identified at baseline (target and non-target) will be reassessed using the same method (CT scan with contrast or MRI) throughout the course of the study;
- All CT scans, MRIs, bone scans, and chest x-rays obtained on all patients enrolled at the site should be reviewed by the local radiologist who, together with the investigator, will determine the local assessment of response and progression;
- If skin lesions are used for tumor assessment, the corresponding photos must also be transmitted/delivered to the local radiologists.

7.6 Safety

Safety assessments will consist of monitoring and recording all AEs, including SAEs, the regular monitoring of hematology, serum chemistry, routine monitoring of vital signs (heart rate, blood pressure, and body temperature), and chest x-rays, ECGs, and physical condition.

Toxicity will be assessed using the National Institutes of Health (NIH) NCI-CTCAE, version 3.0 (CTCAE v3.0, [<http://ctep.cancer.gov/forms/CTCAEv3.pdf>]).

7.6.1 Adverse Events

An AE, for the purposes of this protocol, is the appearance of (or worsening of any pre-existing) undesirable sign(s), symptom(s), or medical condition(s) occurring after signing the informed consent, even if the event is not considered to be related to the study drug (study drug refers to the drug under evaluation [RAD001], and study treatment also refers to RAD001).

Adverse events will be assessed according to the CTCAE, version 3.0. If CTCAE grading does not exist for a particular AE, the severity of mild, moderate, severe, and life-threatening, or grades 1 to 4, will be used. The CTCAE grade 5 (death) will not be used in this study; rather, this information will be collected on the End of Treatment or Survival Information CRF page. All AEs will be coded by System Organ Class (SOC) and preferred term using the Medical Dictionary for Regulatory Activities (MedDRA), latest version.

Adverse event monitoring should be continued for at least 4 weeks following the last dose of study treatment. Adverse events (but not SAEs) occurring before starting study treatment, but after signing the informed consent form, are recorded on the Medical History/Current Medical Conditions CRF pages. Abnormal laboratory values or test results constitute an AE only if they induce clinical signs or symptoms, are considered clinically significant, or require therapy (e.g., any hematological abnormality that requires transfusion or cytokine treatment); and should be recorded on the Adverse Events CRF page under the signs, symptoms, or diagnosis associated with them. In addition, isolated abnormal laboratory values that are considered clinically significant (e.g., cause study discontinuation or constitutes in and of itself a SAE) should be recorded on the Adverse Events CRF page. Serious AEs occurring after signing the Informed Consent are recorded on the Adverse Event CRF page.

The occurrence of AEs should be sought by non-directive questioning of the patient at each visit during the study. Adverse events may also be detected when they are volunteered by the patient during or between visits or through physical examination, laboratory test, or other assessments.

As far as possible, each AE should be evaluated to determine:

1. The severity grade (CTCAE grades 1 to 4);
2. Its relationship to study drug (suspected/not suspected);
3. Its duration (start and end dates or if continuing at final exam);
4. Action taken (no action taken; study drug dosage adjusted/temporarily interrupted; study drug permanently discontinued due to this AE; concomitant medication taken; non-drug therapy given; hospitalization/prolonged hospitalization);
5. Whether it is serious, where a SAE is defined as one which:
 - Is fatal or life-threatening;
 - Results in persistent or significant disability/incapacity;
 - Constitutes a congenital anomaly/birth defect;
 - Requires inpatient hospitalization or prolongation of existing hospitalization, unless hospitalization is for:
 - a) Routine treatment or monitoring of the studied indication, not associated with any deterioration in condition (specify what this includes);
 - b) Elective or pre-planned treatment for a pre-existing condition that is unrelated to the indication under study and has not worsened since signing the informed consent;

- c) Treatment on an emergency outpatient basis for an event not fulfilling any of the definitions of a SAE given above and not resulting in hospital admission;
 - d) Social reasons and respite care in the absence of any deterioration in the patient's general condition.
- Is medically significant, i.e., defined as an event that jeopardizes the patient or may require medical or surgical intervention to prevent one of the outcomes listed above.

Unlike routine safety assessments, SAEs are monitored continuously and have special reporting requirements; see [Section 8.1](#).

All AEs should be treated appropriately. Such treatment may include changes in the study drug treatment, including possible interruption or discontinuation, starting or stopping concomitant treatments, changes in the frequency or nature of assessments, hospitalization, or any other medically required intervention. Once an AE is detected, it should be followed until its resolution, an assessment should be made of any changes in its severity at each visit (or more frequently, if necessary), its suspected relationship to the study drug, any of the interventions required to treat it, and its outcome.

Information about common side effects already known about the study drug can be found in the IB or will be communicated between IB updates in the form of Investigator Notifications. This information will be included in the patient informed consent and should be discussed with the patient during the study as needed.

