Metabolic changes (hyperlipidemia and hyperglycemia) may be observed during treatment with RAD001. Both events may be medically managed. Hyperlipidemia has been reported as an apparent drug reaction (ADR) in 10% of patients, although review of the laboratory values suggests that as many as a quarter of the patients developed grade 1 to grade 2 hyperlipidemia on treatment, mostly hypercholesterolemia. Hyperglycemia has been reported as an AE in 7% of patients. Grade 3 hyperglycemia has been observed, especially in diabetics receiving RAD001 treatment. Therefore, patients with diabetes should have their blood glucose monitored carefully and their medications adjusted, as needed, to maintain adequate control of their blood glucose levels.

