6.1.2 Known Undesirable Effects of RAD001

Adverse events most frequently observed with RAD001 are rash, stomatitis/oral mucositis, fatigue, headache, anorexia, nausea, vomiting, diarrhea, ocular toxicity, and infections. Non-infectious pneumonitis has also been observed as indicated in [Section 1.2.3.3](#).

Overall, the most frequently observed laboratory abnormalities include neutropenia, thrombocytopenia, hypercholesterolemia, and/or hypertriglyceridemia. The majority of these AEs have been of mild to moderate severity (CTC grade 1 to grade 2). Refer to [Table 3](#) for management of laboratory abnormalities.

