6.1.3 RAD001 Dose Level Modification/Interruption Guidelines in Case of Suspected Toxicity

Dose adjustments are permitted in those patients who are unable to tolerate the protocol-specified dosing schedule. If administration of RAD001 must be interrupted because of unacceptable toxicity, drug dosing will be interrupted or modified according to rules described in [Table 2](#), [Table 3](#), and [Table 4](#).

If the toxicity is tolerable to the patient, the initial dose should be maintained. If the toxicity is intolerable to the patient, RAD001 treatment is to be interrupted until recovery to grade ≤ 1 , then reintroduced at the initial dose or a lower dose level, depending on toxicity type and grade (see [Table 3](#)). All interruptions or dose modifications must be recorded on the Dosage Administration Record CRF.

Table 2 RAD001 Dose Level Modification Guidelines

Dose Level	Dose Schedule
0	10 mg daily
1	5 mg daily
2	5 mg every other day

Table 3 provides the procedure to be followed for dose modification and re-initiation of RAD001 in the event of toxicities suspected to be related to the study drug.

Table 3 Criteria for Dose Modification in Case of Suspected RAD001 Toxicity

Toxicity	Actions
Non-hematological toxicity	
Grade 1	No dose modification.
Grade 2 (except pneumonitis):	If the toxicity is tolerable to the patient, maintain the same dose. If toxicity is intolerable to the patient, interrupt RAD001 until recovery to grade ≤ 1 , then re-introduce RAD001 at the same dose. If the event returns to grade 2, interrupt RAD001 until recovery to grade ≤ 1 , then re-introduce at the lower dose level.
Grade 3 (except hyperlipidemia):	Interrupt RAD001 until recovery to grade ≤ 1 , then re-introduce at the lower dose level. For pneumonitis, consider the use of a short course of corticosteroids.
Grade 3 hyperlipidemia (hypercholesterolemia and/or hypertriglyceridemia):	Should be managed using standard medical therapies.
Grade 4:	Discontinue RAD001.
Reactivation of HBV or HCV	Please refer to Tables 6 and 7 .
Hematological toxicity	
Grade 1	No dose modification.
Grade 2 thrombocytopenia (platelets $<75 \times 10^9/L$, $\geq 50 \times 10^9/L$):	Interrupt RAD001 until recovery to grade ≤ 1 (platelets $\geq 75 \times 10^9/L$), then re-introduce RAD001 at the initial dose. If thrombocytopenia returns to grade 2, interrupt RAD001 until recovery to grade ≤ 1 , then re-introduce at the lower dose level.

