6.1.4.2 Management of Hyperlipidemia and Hyperglycemia

Treatment of hyperlipidemia should take into account the pre-treatment status and dietary habits of the patient. Blood tests to monitor hyperlipidemia must be taken in the fasting state.

Grade 2 or higher hypercholesterolemia (>300 mg/dL or 7.75 mmol/L) or grade 2 or higher hypertriglyceridemia ($>2.5 \times$ ULN) should be treated with a statin or appropriate lipid-lowering medication, in addition to diet. Patients should be monitored clinically and through

serum biochemistry for the development of rhabdomyolysis and other AEs as required in the product label/data sheets for HMG-CoA reductase inhibitors.

Note: Concomitant therapy with fibrates and an HMG-CoA reductase inhibitor is associated with an increased risk of a rare, but serious, skeletal muscle toxicity manifested by rhabdomyolysis, markedly elevated creatine phosphokinase levels and myoglobinuria, acute renal failure, and sometimes death. The risk versus benefit of using this therapy should be determined for individual patients based on their risk of cardiovascular complications of hyperlipidemia.

Grade 3 hyperglycemia has been observed in patients receiving RAD001 therapy. In many cases in Study RAD001C2222, the affected patients had an abnormal fasting glucose at baseline. Based on this finding, it is recommended that optimal glucose control be achieved before starting a patient on RAD001. Study patients should have their glucose levels monitored during RAD001 therapy.

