7.6.5 Laboratory Evaluations

All standard clinical laboratory analyses described below are performed by local laboratories. The frequency of the assessments is indicated in Table 9. All laboratory procedures including collection of samples, shipment, reporting of results, alerting of extreme values, and notable values are provided in the Laboratory Manual. The local laboratory will provide the sponsor with a copy of the laboratory certification and tabulation of the reference ranges.

Abnormal laboratory values that are clinically relevant (i.e., require a dose modification, interruption, or indicate changes in previously abnormal values) must be recorded on the Adverse Events CRF page. For clinically relevant values from local laboratories, record actual laboratory abnormality value and grade on the local laboratory CRF page only if the severity grade is different from the severity grade reported by the local laboratory.

If a local laboratory value is recorded on the local laboratory CRF page, the site will provide the local laboratory reference range attached to the local laboratory CRF page.

All laboratory results must be available at the time the patient sees his/her attending oncologist.

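### Protocol 7.6.5 sends any change in an already abnormal laboratory value to the adverse event page, while 7.6.1 excludes such a value unless it is symptomatic, treated or judged clinically significant

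*Protocol*

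**What the plan says.** Protocol 7.6.1 is restrictive: "Abnormal laboratory values or test results constitute an AE only if they induce clinical signs or symptoms, are considered clinically significant, or require therapy". It then asks that "isolated abnormal laboratory values that are considered clinically significant (e.g., cause study discontinuation or constitutes in and of itself a SAE") also go on the AE page. Discontinuation and an SAE are examples there, not a closed list.

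Protocol 7.6.5 is mandatory: "Abnormal laboratory values that are clinically relevant (i.e., require a dose modification, interruption, or indicate changes in previously abnormal values) must be recorded" on the AE page. Here the parenthesis is introduced as a definition. It names dose modification, interruption and movement in an already abnormal value. It does not mention symptoms or treatment.

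Neither section refers to the other or says which governs. SAP 8.1 adds no rule for laboratory findings. It defines a treatment-emergent event by start date relative to dosing and summarizes what the AE page holds. Protocol 10.5.2 and SAP 4.2.4 both name AE frequency and laboratory values as the bases of the safety assessment.

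**The concern.** A restrictive rule and a compulsory rule can coexist only if everything that must be recorded also passes the restriction. The third trigger in 7.6.5 fails that test, because it covers changes of any size in either direction. A site that follows 7.6.5 literally fills the AE page with non-events. A site that follows 7.6.1 leaves them off.

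At stake is the meaning of AE incidence, a named safety endpoint, for parameters that are often abnormal when a patient enters. A second, smaller exposure is the SAP 8.1 count of patients whose treatment-emergent event led to a change in study drug. Listing 16.2-3.2 codes a laboratory abnormality separately from an adverse event as the reason for a dose change. A laboratory-driven interruption can therefore appear in the dosing data without any AE.

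**Working it through.** The plan states no figure that rests on this point, so there is none to reproduce. The check is to apply each rule to concrete cases, using the protocol's own management rules only to decide what would happen to the patient.

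| Case | 7.6.1 | 7.6.5 | Result |
|---|---|---|---|
| Abnormal at entry, then moves; no symptom, treatment, dose action or judgment of significance | Not an AE | Must be recorded | Contradiction |
| Same, but the value improves | Not an AE | Must be recorded (no direction given) | Contradiction |
| Asymptomatic grade 2 thrombocytopenia or grade 3 neutropenia, drug interrupted under Table 3 | AE if judged significant | Must be recorded | Judgment against obligation |
| New grade 2 or higher lipid rise, treated, dose unchanged | AE | Not required, not excluded | No conflict |
| Symptomatic value, normal at entry, no treatment or dose action | AE | Not required, not excluded | No conflict |
| Grade 3 hyperglycemia, treated and interrupted | AE | Must be recorded | Agreement |

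**Can the contradictory cases occur?** Yes. Section 5.1 admits hemoglobin just above 9 g/dL, creatinine up to 1.5 times the upper limit of normal, and transaminases up to 2.5 times that limit (5 times with liver metastases). It sets no lipid limit. Chemistry and lipids are then measured on Day 1 of every cycle, so some movement in an abnormal value is to be expected.

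**Does the third case matter for this drug?** Section 6.1.2 says that "the most frequently observed laboratory abnormalities include neutropenia, thrombocytopenia, hypercholesterolemia, and/or hypertriglyceridemia". The two blood-count items are those for which Table 3 calls for interruption at a given grade whether or not there are symptoms.

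**Scale.** For one AE term, the shift in patient-level incidence is m/N. Here m is the number of patients whose only record of that term comes from the undirected trigger. One such patient moves the rate by 1/110 = 0.9 percentage points at the protocol's planned size, or 1/142 = 0.7 points at the SAP's. The documents give neither m nor the share of patients abnormal at entry, so neither the total shift nor an upper bound can be calculated.

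**The case against.** The best defense is that the sections can mostly be read together, and much of it stands.

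- **Treated lipids.** A reader might infer that a lipid rise managed with medication and no dose change is an AE in one section and not in the other. Section 6.1.4.2 says such patients "should be treated with a statin or appropriate lipid-lowering medication, in addition to diet", and Table 3 says of grade 3 hyperlipidemia: "Should be managed using standard medical therapies". But 7.6.5 only sets a minimum. It removes nothing that 7.6.1 makes an AE, so there is no conflict.
- **Dose interruption.** The significance criterion in 7.6.1 is open, and 7.6.1 itself lists dose adjustment and interruption among the actions taken for an AE. A careful investigator can bring an interruption under it. What remains is judgment against obligation, not contradiction.
- **Worsening.** The general AE definition in 7.6.1 already covers worsening of a pre-existing condition. That narrows the gap, but it cannot cover an improving value or a change nobody thinks significant.
- **Earlier hyperlipidemia rates.** Section 1.2.3.3 says "Hyperlipidemia has been reported as an apparent drug reaction (ADR) in 10% of patients", while laboratory review suggested up to a quarter. In 110 patients that is 110 × 0.10 = 11 against 110 × 0.25 = 27.5. It is tempting to take this gap as the size of the problem. It compares reported reactions with laboratory review, not 7.6.1 with 7.6.5. A new, untreated, asymptomatic grade 1 rise with no dose change meets no explicit trigger in either section when it first appears, so that part of the gap is the same under both rules.
- **Comparability.** A reader might conclude that AE rates cannot be compared between sites or with earlier studies of the drug. Section 10 pools the centers and plans no site comparison, and the documents do not give the AE rules of the earlier studies.
- **Laboratory data.** SAP 8.3 grades hemoglobin, platelets, neutrophils, creatinine, transaminases, glucose, cholesterol and triglycerides from laboratory results. These summaries do not use the AE page and stand under either rule.

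It could also be said that 7.6.5 only tells sites where to write a value down. But SAP 8.1 has no step that removes entries failing 7.6.1, so an entry on the AE page dated on treatment is counted.

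**Conclusion.** The inconsistency is real but narrow. For a value abnormal at entry that changes without symptoms, treatment, dose action or a judgment of significance, the two sections cannot both be followed. For an asymptomatic value that leads to a dose change, one section compels recording and the other leaves it to the investigator.

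The affected results are AE incidence for such parameters and the count of events leading to a change in study drug. The size is unknown and cannot be derived from the documents. CTC-graded laboratory summaries, the primary endpoint and the sample size are untouched.

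This assumes that sites read 7.6.5 literally. A site that reads its definition as an illustration of clinical significance would produce few or none of the extra entries.

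**What to change.** 1. State one rule, in 7.6.1. Add *requires dose modification or interruption* to its list as a trigger for AE recording.
2. In 7.6.5, replace the parenthetical definition with a reference to 7.6.1.
3. Replace the undirected trigger with a clinically significant worsening from baseline, for example a worsening in CTC grade that the investigator judges clinically significant. Deleting the trigger outright would lose a useful prompt to record worsening of a pre-existing abnormality.

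The cost is a few lines of wording and a note to sites. Some minor changes in already abnormal values would no longer be AEs. Grade changes in patients already graded at screening stay visible in the shift tables. Changes within a grade, and parameters without a CTC grade, would be seen only in the by-visit summaries and listings.

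The SAP output shells are dated 22SEP2017, against a planned last visit of 30 January 2012 in protocol Table 10, so data collection may already be complete. In that case, disclose the dual rule wherever AE rates for these parameters are reported, and use CTC-graded laboratory data as their main incidence summary. Before relying on the shift tables for this, add a Grade 0 screening column. The shells show screening Grades 1 to 4 only, so patients normal at screening have no column of their own.
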